## **STUDY ENDPOINTS:**

Primary endpoints:

- Change in locomotion efficiency as measured by the 6-Minute Walk West (6MWT)

Secondary endpoints

- Change in Ten Meter Walk Test (10MWT) at self-selected velocity and fastest (safe) velocity
- Change in maximum volitional isokinetic and isometric ankle and knee torque as measured by the Biodex dynamometer strength assessment
- Change in transfers
- Change in bilateral lower extremity strength

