### **PROCEDURES INVOLVED:**

Study Design: A randomized, controlled crossover trial. We are evaluating the effectiveness of AIH prior to transcutaneous spinal cord stimulation during locomotor training on improving ambulation and standing balance among individuals with paraplegia or tetraplegia due to spinal cord injury. All participants will complete three arms of the study:

1. AIH prior to transcutaneous spinal cord stimulation during locomotor training (AIH + tSCS)
2. Sham AIH prior to sham transcutaneous spinal cord stimulation during locomotor training (SHAM + SHAM)
3. Sham AIH prior to transcutaneous spinal cord stimulation during locomotor training (SHAM AIH + tSCS)

Participants will complete a 4-week washout period between each arm.

Prior to Visit 2, a medical clearance letter describing study procedures and risks will be sent to the subject's physician or clinician to request medical clearance for the subject to participate in the study. Permission to contact the participant's physician or clinician to obtain medical clearance will be obtained during the screening process.

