#### STATISTICAL ANALYSIS PLAN:

All functional gait outcomes will be assessed at three follow-up visits. We will use a linear mixed model with repeated measures to jointly assess changes at INT5, POST and 1WK relative to baseline within each arm as well as assess the changes between arms for each time point. The model will include time points (BL, INT5, POST, and 1WK as a categorical variable) and treatment arm (AIH + tSCS, SHAM AIH + tSCS, and SHAM + SHAM as categorical variable) as fixed effects and subject as a random effect. Linear mixed models provide a better mechanism for handling missing data by using all available data, rather than performing a complete case

analysis, if the data are assumed to be missing at random. The level of significance will be set at alpha = 0.05. Bonferroni corrections will be used to adjust for multiple comparisons.

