**SAMPLE SIZE AND POWER CONSIDERATIONS:**

The sample size calculation will be based on a one-sided paired *t*-test comparing the changes in self-selected speed of the 10 meter walk test from pre- to 1 week post-treatment. Based on the minimum clinically important difference (MCID) for speed previously reported in SCI29, we want to detect a change in speed of 0.06 m/s. The standard deviation of the change from baseline to 1 week post was 0.07 m/s. Therefore, using 0.857 as our effect size, a sample size of n=10 will provide a power of 80% with alpha = 0.05.

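### The crossover model lists no arm × time term, no period term and no within-period covariance; as listed it cannot estimate the differences in change that the plan sets out to assess

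*Combined protocol and SAP*

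**What the plan says.** Procedures Involved describes the design as "A randomized, controlled crossover trial" in which every participant goes through all three arms, with four weeks of washout between them. Study Timelines gives each arm its own baseline assessment, a post-treatment assessment and a one-week follow-up. Study Endpoints defines the primary endpoint as a change in the 6MWT.

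The only analysis model is in the Statistical Analysis Plan section. It is a "linear mixed model with repeated measures to jointly assess changes at INT5, POST and 1WK relative to baseline within each arm", and it is also meant to "assess the changes between arms for each time point". The terms are then enumerated: time point (four categories) and treatment arm (three categories) "as fixed effects and subject as a random effect". No arm × time interaction, period or sequence term, subject-by-period effect or covariance structure is given there or elsewhere. On multiplicity, "Bonferroni corrections will be used to adjust for multiple comparisons", with no family defined.

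Sample Size and Power Considerations uses a change outcome for a different variable, "comparing the changes in self-selected speed of the 10 meter walk test from pre- to 1 week post-treatment", and states that "The standard deviation of the change from baseline to 1 week post was 0.07 m/s".

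**The concern.** The quantity of interest is a difference between arms in change from baseline. In a model with arm and time as main effects only, that difference is fixed at zero whatever the data show, so the listed terms and the stated aim do not fit together.

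Adding the interaction leaves a second gap. Each participant contributes three blocks of visits, and visits in one block may resemble each other more than visits in different blocks. Walking level may also drift from period to period, since participants train in every arm. If the model has only a subject intercept and no period term, both sources go into the residual variance. They largely cancel from a within-period change but still inflate its estimated standard error. At stake are the estimability of the named contrast and, beyond that, some power.

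**Working it through.** **Inputs from the documents.** 36 participants (Study Summary); three arms per participant (Procedures Involved); four time points, BL, INT5, POST and 1WK (Statistical Analysis Plan); 0.06 m/s to detect and 0.07 m/s SD of change (Sample Size and Power Considerations).

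**Assumed, because the documents give no figure.** The within-period covariance, any period trend, balanced sequences, a between-arm difference of 0.06 m/s, and a Bonferroni family of 9 (3 arm pairs × 3 follow-up visits). Tests are two-sided from step 2 on.

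**1. The plan's own figure.** d = 0.06/0.07 = 0.857. An exact one-sided paired t-test at 0.05 has 80.4% power with n = 10 and 75.8% with n = 9, so the stated n = 10 reproduces. It does not depend on the model examined here.

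**2. Listed terms only.** The modelled mean for arm a at time t is μ + α_a + τ_t. The change from baseline is τ_t − τ_BL, which does not involve a, so the difference in change between any two arms is 0 at every visit. As a noiseless example, let one arm gain 0.06 m/s at all three follow-ups and the others gain nothing:

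- Additive model: change of 0.06/3 = 0.02 in every arm, difference in change 0.00, and a constant arm gap of 0.06 × 3/4 = 0.045 at all visits, including baseline.
- With arm × time: change of 0.06 in the one arm, 0.00 in the others, difference 0.06.

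**3. Arm × time added, subject intercept only.** Let V be the covariance of the T visits in a period, with periods independent given subject. The pooled residual variance has expectation

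s² = [3·tr(V) − 3·sum(V)/(3T)] / (3T − 1),

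and the estimated-to-true SE ratio for the change contrast at visit k is √[2s² / (V₀₀ + V_kk − 2V₀k)].

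For V = I + rJ (r = subject-by-period to residual variance ratio) and T = 4, s² = 1 + 8r/11 and the ratio is √(1 + 8r/11):

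| r | SE ratio | Actual alpha at nominal 5% |
|---|---|---|
| 0 | 1.000 | 5.0% |
| 0.25 | 1.087 | 3.3% |
| 0.5 | 1.168 | 2.2% |
| 1 | 1.314 | 1.0% |

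Alpha is 2[1 − Φ(1.96 × ratio)]. Simulation (4000 trials per case, n = 36) gave 5.1/3.4/2.6/1.3%. With the three assessments in Study Timelines (T = 3) the ratio is √(1 + 6r/8) = 1.000/1.090/1.173/1.323.

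**4. Serial correlation instead.** For AR(1) with ρ = 0.1/0.2/0.3, T = 4 and equally spaced visits, the ratio at 1WK is 0.993/0.988/0.988 (alpha 5.2 to 5.3%): no loss, and an SE about 1% too small. At INT5 it is 1.046/1.100/1.165. Equal spacing is doubtful for INT5, because Study Timelines lists no separate INT5 assessment and the five sessions can fall within one week. At ρ = 0.5 the 1WK ratio is 1.016.

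**5. No period term.** Take r = 0 and a level shift of d m/s per period. The residual variance per visit is 0.07²/2 = 0.00245 on 36 × 12 − 36 − 11 = 385 df, so the expected residual sum of squares is 0.943. The trend adds 36 × 4 × 2d². For d = 0.02/0.03/0.05 that is 0.115/0.259/0.720, giving SE ratios √(1 + added/0.943) = 1.059/1.129/1.328. In a separate simulation at d = 0.03 the mean SE rose from 0.0165 to 0.0186 and type I error fell to about 3%; adding period restored about 5%.

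**6. What this could mean for power, as illustration.** True SE at 1WK = √(2 × 0.07²/36) = 0.0165; power = Φ(0.06/0.0165 − z × ratio). At r = 0/0.25/0.5/1:

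- z = 1.96: 95/93/91/86%.
- z = 2.77 (0.05/9): 81/73/66/50%.

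With a correct SE, power would stay at the first value in each row.

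**The case against.** The strongest reply is that the sentence before the list states the purpose: changes within each arm and between arms at each visit. Neither can be obtained without arm × time, so an analyst following the purpose would fit it. This stands in part. A reader might infer that the planned analysis is bound to return zero; the documents do not support that, because the aim points to the interaction. But the sentence that names the terms leaves it out. Reading the aim as raw arm differences at each visit does not help, since the additive model gives one constant gap shared by all visits, baseline included.

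A reader might also infer inflated type I error from testing the arm main effect under within-period correlation. The plan names no such test, so that is no support for the point.

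The reference to repeated measures is compatible with a residual covariance, so the subject-intercept-only model in steps 3 to 6 is one possible reading. No structure is named, however. Omitting period could be read as biasing the arm comparison; with balanced sequences it costs precision only, and the documents do not give the sequences. Lastly, the 50% power figure needs three assumptions together: r = 1, nine comparisons, and 0.06 m/s as a between-arm difference (the plan states it only as a change in speed). Without the correction, power at 36 participants stays at 86 to 95%. All of this stands as a limit on size.

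**Conclusion.** The point holds as an incomplete model specification that should be fixed before analysis. That the listed terms cannot deliver the stated contrasts is exact algebra and needs no assumed figure.

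The second part, loss of precision if arm × time is added with a subject intercept alone and no period term, is conditional. It ranges from none to an SE about 31% too large over the variance ratios tried, and from 6 to 33% too large over the period trends tried. Under weak AR(1) correlation there is essentially no loss at 1WK, the visit used for the sample size. The usual direction is conservative. All these figures rest on assumed covariances and trends, and the power figures concern 10MWT speed. No SD is given for the 6MWT, so nothing can be quantified for the primary endpoint.

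**What to change.** In the Statistical Analysis Plan section:

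- List arm, time, arm × time, period and period × time as fixed effects, and state that the arm × time contrasts carry the treatment comparison.
- Keep subject as a random effect and specify the within-period covariance as unstructured, with a subject-by-period random intercept as the fallback if it does not converge.
- Optionally add, as a sensitivity analysis, change from each period's own baseline with arm and period fixed and subject random. This is not equivalent when visits are missing: it drops a period with no baseline, whereas the plan chose a mixed model in order to use all available data.

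The cost is wording and a few degrees of freedom: 2 for period and 2 × 3 = 6 for period × time. No visits or data are added. With no within-period correlation, simulated power at 0.05/9 falls from about 80% to 79% when subject-by-period variation is removed and period × time is included, and to about 77% with change scores. Change scores also lose a little at 1WK under AR(1) 0.3 (82% to 79%). At variance ratios of 0.5 and 1, removing subject-by-period variation and including period × time restores type I error to about 5% and power to about 79 to 80%. The unstructured covariance itself was not simulated, so its exact cost is not known.

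### Holm's step-down procedure would give the same familywise error control as the planned Bonferroni correction, with equal or greater power on the contrasts that isolate AIH and tSCS

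*Combined protocol and SAP*

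**What the plan says.** STATISTICAL ANALYSIS PLAN specifies a linear mixed model with "treatment arm (AIH + tSCS, SHAM AIH + tSCS, and SHAM + SHAM as categorical variable) as fixed effects", time as a categorical factor and subject as a random effect. It will assess changes at INT5, POST and 1WK "relative to baseline within each arm as well as assess the changes between arms for each time point". On error control it says "The level of significance will be set at alpha = 0.05" and "Bonferroni corrections will be used to adjust for multiple comparisons". It names no step-down variant, does not say which comparisons form the family, and does not say whether the model's tests are one- or two-sided.

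PROCEDURES INVOLVED describes a crossover: "All participants will complete three arms of the study". Between-arm contrasts are therefore within-person. The same section states the aim as the effectiveness of giving AIH before tSCS, which is the AIH + tSCS against SHAM AIH + tSCS contrast.

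STUDY ENDPOINTS makes the 6MWT primary and the 10MWT secondary. STUDY SUMMARY and PARTICIPANT POPULATION(S) plan 36 participants.

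**The concern.** Single-step Bonferroni holds every comparison to the same strict threshold, whatever else has been rejected. With three pairs of arms that threshold is 0.0167. Holm relaxes it for the remaining comparisons each time one is rejected.

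The arms here are nested: no active component, tSCS alone, then tSCS plus AIH. If both components help, AIH + tSCS against SHAM + SHAM carries the sum of the two effects and tends to reject first. Under Holm that eases the thresholds for the two contrasts that attribute benefit to AIH or to tSCS. Bonferroni gives up this easing and gets no tighter error control in return.

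The within-arm tests raise a related point. Every arm includes locomotor training, so a change from baseline within an arm cannot separate AIH or tSCS from training. If these tests are counted in the family, they tighten the threshold for the contrasts that can.

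**Working it through.** **1. The plan's own figure.** SAMPLE SIZE AND POWER CONSIDERATIONS says "The sample size calculation will be based on a one-sided paired" t-test on the 10MWT, that "we want to detect a change in speed of 0.06 m/s", and that "The standard deviation of the change from baseline to 1 week post was 0.07 m/s". The effect size is 0.06/0.07 = 0.857. With n = 10 the noncentrality is 0.857 × √10 = 2.71 on 9 degrees of freedom, and one-sided power at 0.05 is 80.35%. The stated 80% reproduces. It uses an unadjusted alpha, and the documents give no power under any multiplicity correction.

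**2. Why Holm cannot lose.** With m tests, Bonferroni rejects when p ≤ 0.05/m. Holm orders the p-values and compares them in turn with 0.05/m, 0.05/(m−1), …, 0.05, stopping at the first failure. If p ≤ 0.05/m, every smaller p-value also meets 0.05/m and so passes its own equal or looser Holm threshold. Every Bonferroni rejection is thus a Holm rejection. For m = 3 the thresholds are 0.0167 throughout (Bonferroni) against 0.0167, 0.025 and 0.05 (Holm). In simulation with no true effects, Holm made at least one rejection in about 4.4% of trials.

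**3. Inputs for the size of the gain.**
- From the documents: n = 36; SD of change 0.07 m/s (10MWT, baseline to 1 week post); three arms, hence three pairs.
- Assumed: two-sided tests; one time point; between-arm correlation of changes ρ from 0 to 0.7; additive component effects; normal data; no carryover, period effect or dropout; paired t-tests standing in for the model contrasts.
- SD of a between-arm difference in change = 0.07 × √(2(1 − ρ)): 0.099 at ρ = 0, 0.083 at 0.3, 0.070 at 0.5 and 0.054 at 0.7.

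**4. Gain of Holm over Bonferroni on the AIH contrast** (percentage points of power, simulated):

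| AIH effect / tSCS effect (m/s) | ρ = 0 | ρ = 0.3 | ρ = 0.5 | ρ = 0.7 |
|---|---|---|---|---|
| 0.06 / 0.06 | 8 | 2.6 | 0.5 | 0 |
| 0.03 / 0.03 | 8 | 11 | 14 | 11 |
| 0.02 / 0.04 | 6 | 10 | 14 | 18 |
| 0.06 / 0 | 3 | 1 | under 1 | 0 |
| 0.03 / 0 | 2 | 2.5 | 3 | 3 |

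Some of the underlying power levels, Bonferroni to Holm:
- 0.03 / 0.03: 53% to 67% at ρ = 0.5, and 26% to 34% at ρ = 0.
- 0.06 / 0.06: 99.4% to 99.9% at ρ = 0.5, and 86% to 94% at ρ = 0.
- 0.06 / 0: 99.4% to 99.7% at ρ = 0.5, and 86% to 89% at ρ = 0.

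Where the two effects are equal, the tSCS contrast has the same power and gain as the AIH contrast, apart from simulation error.

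**5. A larger family.** The plan's three follow-ups give 3 pairs × 3 visits = 9 between-arm tests and 3 arms × 3 visits = 9 within-arm tests per outcome. For a family of the 9 between-arm tests (contrast SD 0.07, assumed correlation over time 0.6, two-sided, n = 36), power on one AIH test rises from 37% to 52% with 0.03 / 0.03, and from 98% to 99.8% with 0.06 / 0.06. The direction is the same, and the size again depends on the effects.

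**The case against.** Bonferroni is a valid and familiar method, and it comes with matching simultaneous confidence intervals, which Holm does not offer in simple form. At the planned 36, if each component adds the 0.06 m/s used in the sample size section, power is already high and the gain is under 1 point at ρ = 0.5. If only one component works, little is freed. Holm is not the most powerful choice either: for three pairwise contrasts, Shaffer's step-down (0.0167, 0.05, 0.05) gave 70% against Holm's 67% in the 0.03 / 0.03 case at ρ = 0.5. Every figure rests on the secondary 10MWT, because no SD is given for the 6MWT. Without a defined family, neither method can be applied.

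All of this stands as a limit on the size and weight of the point. It does not make Bonferroni preferable for testing, since Holm never rejects less. The 0.06 m/s in the plan is also a pre-to-post change and not a between-arm increment. If it is the whole change in the combined arm, and neither training nor either component does harm, the two increments together cannot exceed 0.06, and that is where the gain is larger.

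Three stronger readings are tempting, and the documents support none of them:
- *Bonferroni costs this trial some 10 to 16 points.* That follows only from particular effect sizes and correlations, none of which the plan gives.
- *The AIH contrast is the one most likely to be missed.* Nothing in the documents makes the AIH effect smaller than the tSCS effect, and with equal effects the two contrasts have equal power.
- *The within-arm tests use up the same correction.* The family is undefined, so this is possible but not stated.

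**Conclusion.** The point holds as an efficiency improvement. Replacing Bonferroni with Holm keeps strong familywise control at 0.05, cannot lower power on any contrast, and in the three-test scenarios examined at n = 36 raises power on the AIH contrast by about 0 to 18 points. By scenario the gain is about 8 to 14 points if 0.06 m/s splits evenly between the components, 0 to 8 if each adds 0.06 m/s, and 0 to 3 if only AIH works.

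These ranges rest on the 10MWT SD and the assumptions listed above. The gain for the primary 6MWT cannot be calculated from the documents. The planned method is not an error, and no conclusion drawn under it would be invalid. The undefined family is the gap to close first, whichever method is kept.

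**What to change.** Replace the Bonferroni sentence with: *Between-arm comparisons of change in the primary outcome (6MWT) at the stated time point(s) will be adjusted with the Holm step-down procedure at familywise alpha 0.05.* Name the time point or points explicitly. For three pairs of arms at one time point, compare the ordered p-values with 0.0167, 0.025 and 0.05, stopping at the first that fails. Report within-arm changes as estimates with intervals, outside that family.

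The cost is one or two sentences, settled before outcome data are seen, with no added participants or visits. The drawback is that Holm has no simple matching simultaneous intervals. Report Bonferroni or unadjusted intervals beside the tests and say which they are; in some cases they will not agree with the Holm decision.

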**SAMPLE SIZE AND POWER CONSIDERATIONS:**

The sample size calculation will be based on a one-sided paired *t*-test comparing the changes in self-selected speed of the 10 meter walk test from pre- to 1 week post-treatment. Based on the minimum clinically important difference (MCID) for speed previously reported in SCI29, we want to detect a change in speed of 0.06 m/s. The standard deviation of the change from baseline to 1 week post was 0.07 m/s. Therefore, using 0.857 as our effect size, a sample size of n=10 will provide a power of 80% with alpha = 0.05.

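### The sample size is calculated for a one-sided, unadjusted test of a secondary endpoint that the analysis plan does not run, and no primary 6MWT contrast or Bonferroni family is named

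*Combined protocol and SAP*

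**What the plan says.** Under Study Endpoints the primary endpoint is "Change in locomotion efficiency as measured by the 6-Minute Walk West (6MWT"), with no visit, arm comparison or test attached. Ten-metre walk speed is listed as secondary.

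Sample Size and Power Considerations rests on a one-sided paired t-test "comparing the changes in self-selected speed of the 10 meter walk test from pre- to 1 week post-treatment". Its inputs are "we want to detect a change in speed of 0.06 m/s" and "The standard deviation of the change from baseline to 1 week post was 0.07 m/s", and its result is "using 0.857 as our effect size, a sample size of n=10 will provide a power of 80% with alpha = 0.05". Alpha is not divided. The Study Summary and the Participant Population table plan 36 participants; no calculation links 10 to 36.

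The Statistical Analysis Plan states: "All functional gait outcomes will be assessed at three follow-up visits". A linear mixed model is to assess "changes at INT5, POST and 1WK relative to baseline within each arm as well as assess the changes between arms for each time point", at alpha 0.05 with sidedness not stated, and "Bonferroni corrections will be used to adjust for multiple comparisons". The listed fixed effects are time point (four levels) and arm (three levels), with subject random. Neither an arm-by-time term nor a count of comparisons is given.

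Study Timelines schedules, for each arm, a baseline visit, one assessment after the last session and one a week later. The INT5 time point appears only in the Statistical Analysis Plan.

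**The concern.** A power statement is useful only if it describes the test that will decide the trial. Here it differs from the planned analysis in endpoint, sidedness, alpha and method. The primary endpoint has no sample size calculation of its own.

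The larger consequence is for interpretation. With three arms, up to three follow-up visits and both within-arm and between-arm comparisons, 6MWT can be tested in many ways. The plan does not say which one decides the trial or what Bonferroni divides by. If those choices are made after the data are seen, they can determine whether the primary result is called positive.

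**Working it through.** **Method.** Power of a paired t-test from the noncentral t distribution, with df = n − 1 and noncentrality d√n. This approximates a mixed-model contrast, ignoring period and carryover effects.

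**1. Reproduce the plan's figure.** Effect 0.06 m/s and SD 0.07 m/s (Sample Size and Power Considerations) give d = 0.06/0.07 = 0.857. At n=10, one-sided 0.05, power is 80.3%, and 10 is the smallest n that reaches 80%. The plan's arithmetic is correct.

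**2. Same inputs under other rules.** The last column takes 0.07 m/s as the SD of change within each arm, with changes uncorrelated between arms (an assumption). The between-arm SD is then 0.07√2 and d = 0.857/√2 = 0.61.

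| Rule | Power, n=10, d=0.857 | Power, n=36, d=0.857 | Power, n=36, d=0.61 |
|---|---|---|---|
| One-sided 0.05 | 80.3% | 99.97% | 97% |
| Two-sided 0.05 | 68% | 99.9% | 94% |
| Two-sided 0.05/3 | 46% | 99.4% | 86% |
| Two-sided 0.05/18 | 18% | 96.5% | 66% |

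The claim for n=10 therefore holds only for the test as sized. The planned 36 is ample on the direct reading of the inputs under every rule shown.

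**3. How many comparisons the analysis section implies.** Within arm: 3 arms × 3 visits = 9. Between arms: 3 pairs × 3 visits = 9. The total is up to 18 per outcome. If 6MWT is not measured at INT5, which the visit schedule does not list, there are two follow-up visits: 6 + 6 = 12. Three arm pairs at a single visit would give 3. The documents state none of these counts.

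**4. What the divisor does to 6MWT at n=36.** Effects are in SDs of the within-participant difference in change, because the documents give no 6MWT effect or SD. The smallest significant observed effect is the critical t (df 35) divided by √36 = 6. True effects of 0.4 to 0.6 SD are assumed. All tests are two-sided.

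| Alpha | Critical t | Smallest significant effect | Power at 0.4 / 0.5 / 0.6 SD | Effect detectable with 80% power |
|---|---|---|---|---|
| 0.05 | 2.03 | 0.34 SD | 65 / 83 / 94% | 0.48 SD |
| 0.05/3 | 2.51 | 0.42 SD | 46 / 69 / 85% | 0.56 SD |
| 0.05/12 | 3.07 | 0.51 SD | 27 / 48 / 70% | 0.66 SD |
| 0.05/18 | 3.22 | 0.54 SD | 23 / 43 / 65% | 0.68 SD |

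At a true 0.5 SD, the share of trials whose verdict differs between /3 and /18 is 68.5% − 42.8% = 26%. Between /3 and /12 it is 68.5% − 48.4% = 20%.

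**5. Can the listed model give the contrast?** With arm and time as additive effects only, the change over time is the same in every arm and the arm difference is the same at every time point. Such a model cannot estimate a difference between arms in change at a given visit. The section's prose asks for such differences; its list of terms does not provide them.

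**The case against.** The strongest reply is that the sample size section only sizes the trial. It is not a decision rule for 6MWT, and the Statistical Analysis Plan alone governs the analysis. That is right. A reader might infer that the two sections give rival rules for 6MWT, one-sided 0.05 against two-sided 0.05/18, so that nearly half of trials (90.3% − 42.8% = 47.5% at 0.5 SD) would have opposite verdicts. The documents do not support this, because nothing carries the one-sided test over to 6MWT. Setting an undivided two-sided 0.05 against /18 is also an extreme pairing, since the plan says that a correction will be applied. The defensible comparison is between plausible divisors, such as 3 and 18.

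A second reply is that 36 is far more than 10. This also stands: on the plan's own inputs power at 36 is at least 96.5%, and the verdict would differ between one-sided 0.05 and two-sided 0.05/18 in only about 3% of trials (99.97% − 96.5%). But 0.857 is a 10-metre walk figure and says nothing about 6MWT. A larger sample does not identify which test is primary.

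Third, 18 is an upper count, and the 0.5 SD effect is assumed. Both are true, which is why 12 comparisons and a range of 0.4 to 0.6 SD are shown. The absence of a named contrast and family depends on neither.

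**Conclusion.** The concern holds as a mismatch between the power statement and the planned analysis, together with an unspecified primary test. The 80% at n=10 belongs to a one-sided, unadjusted 10-metre walk test that the plan does not run. For 6MWT, the arm pair, visit, sidedness and Bonferroni family are all missing, and the listed model cannot estimate the between-arm contrast the prose describes.

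At 36 the significance threshold moves from 0.42 SD (divisor 3) to 0.54 SD (divisor 18), and about 26% of trials change verdict between them at an assumed 0.5 SD.

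A reader might infer that the trial is underpowered. The documents do not show that: 36 covers the stated inputs read directly. The 66% figure at 0.05/18 needs the added assumption that 0.07 m/s is a within-arm SD with no correlation between arms. The 6MWT figures rest on the paired-t approximation and on an assumed effect, since the plan gives none.

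**What to change.** Before any outcome data are seen:

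1. In Study Endpoints and the Statistical Analysis Plan, name one primary contrast: the difference in change in 6MWT between two named arms at one named visit, with stated sidedness, at alpha 0.05. The design description points to AIH + tSCS versus SHAM AIH + tSCS, and the sample size section points to 1 week, but neither says so for 6MWT; the choice is the sponsor's. Make all other comparisons secondary, with a stated Bonferroni family.
2. Add the arm-by-time interaction to the model, and reconcile INT5 with the visit schedule.
3. Replace the n=10 statement with the power of the named test at 36: 80% for 0.48 SD of the within-participant difference in change (two-sided 0.05, paired-t approximation). If several primary comparisons are kept, state 0.56 SD for three or 0.68 SD for 18. Label the 10-metre walk calculation as secondary, and say whether 0.06 m/s is a pre-post change or a between-arm difference.

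This needs no more patients, visits or assessments. The cost is that other 6MWT arm pairs and visits become secondary, so an effect seen only there cannot carry the trial. At a true 0.5 SD, one named two-sided test at 0.05 has 83% power, against 69% with a divisor of 3; the gain is larger only against stricter divisors. If only 30 participants complete, the effect detectable with 80% power by the one named two-sided test rises to 0.53 SD.
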